Children, Youth, and their legal guardian(s). We will recruit approximately 3 youth clients per therapist for a total of 405 youth clients (if younger than 18 years old, we will also obtain written or verbal consent from the client's legal guardian)*. We base our projections for youth clients on administrative data from Medicaid claims. Youth clients range in age from 7-24 with a variety of presenting disorders. Based on these data, we anticipate that youth will be 55% male, and primarily African American or Hispanic/Latino. Any randomly selected child aged 7-24 who is presenting for treatment for any psychosocial difficulties may participate if appropriate assent and/or consent is ascertained. Exclusion criteria include if the child does not have a legal guardian who is able to consent (e.g., DHS is the guardian).

*Note, our intention is to enroll three youth clients per therapist. However, we will ask therapists immediately following the session if this was a “crisis” session or therapy as usual. We are looking for at least three samples of behavior that are not crisis sessions so we can code their behavior; therefore, we may need to enroll more than three clients per therapist if there are sessions that are deemed to not meet criteria for inclusion. Sessions need to include at least ten minutes where the client is in the room (i.e., guardian only sessions will not be counted towards the three sessions needed for this study).

The study will begin human subject activities in Fall 2016 (following full approval from the City of Philadelphia IRB) and continue enrolling human subjects until mid-2020.

PROCEDURES

Aim 1: We will recruit therapists in the City of Philadelphia who (1) have been trained in CBT through a city sponsored CBT initiative, (2) respond to a brief screening survey that they use CBT; and/or (3) are nominated by a supervisor as a therapist who uses CBT. More than 300 therapists from 30 agencies have been trained over the past 7 years, and 40-60 new therapists in 2-5 new agencies are added annually. Therapists participate in training as part of their agency employment; they will not be required to participate in this study to receive training. Therapists, agency leadership, and DBH have expressed considerable enthusiasm for the proposed study. We have included letters of support from agency administrators as well as the DBHIDS Commissioner, [name].

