Therapists will be consented during a study meeting at each agency where we will provide lunch and information about the study. At that meeting, the manager of research projects, with the assistance of the biostatistician, [name], will randomize therapists into one of the three measurement arms. To maintain balance, we will ensure that we have equal numbers of therapists in each study arm in each site.

Therapists report approximately 30 client encounters per week. We base our projections for youth clients on administrative data from Medicaid claims. On average, youth attend 5.7 sessions (SD = 8.6). Our recruitment goal is 3 unique encounters (i.e., separate clients who each had a CBT session) per therapist for a total of 405 youth client encounters. We will use sequential sampling to identify client encounters to include in the trial. We will sample as a function of individual client session number to ensure that we enroll clients receiving services across the treatment span because CBT techniques used in sessions early on in treatment are different than those used later in treatment. For example, treatment of anxious youth would typically begin with psychoeducation and rapport building in initial sessions before progressing to exposure strategies later in treatment. Once therapists are enrolled in the study, our research staff will work with the therapists directly each week to provide the information they need to check in with eligible families for participation (e.g., recruitment notice, script to obtain verbal assent/consent for the research team to approach the family). Because of our desire to randomly sample treatment sessions from different treatment stages (2-9 (early treatment) and 10+ (late treatment)), we will first randomly select the days the research staff will be present at the agency and then randomly select the blocks of time within each day (per each therapist’s schedule) during which the research staff will enroll clients for each therapist. For instance, if we randomly select Monday, Tuesday and Wednesday as the days the

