research staff will be at the agency that week and a therapist participant planned to be at the agency from 11 AM to 7 PM each of those days, then we would randomly select either the first block (11 AM to 3 PM) or the second block (3 PM to 7 PM) of time in which to approach clients of that therapist. Before each block of time begins, the research staff will check in with the therapist to determine how many of the clients scheduled for that block of time are eligible (i.e. youth clients 7-24 years with whom the therapist uses CBT strategies). We will also ask the therapist to indicate if the client is in early or late treatment stages. We will ask therapists to introduce the study to eligible clients within each randomly selected block of time until three clients have been enrolled. We will provide \$25 compensation to complete this process until 3 separate clients who each had a CBT session are enrolled (we will not include if the therapist identifies the session as a crisis of the week session). Based on conversations with our community advisory board, we have been advised that we will need to be flexible at each agency with regard to how we ascertain this information.

We will not have research staff directly approach families to avoid confidentiality concerns. Therapists will approach the family and obtain verbal consent and assent for the research team to contact the family. Any randomly selected child aged 7-24 who is presenting for treatment for any psychosocial difficulties may participate. Exclusion criteria include if the child does not have a legal guardian who can consent to their participation (e.g., DHS-involved youth). Children and their families will be recruited and retained with the help of study team members who will be embedded within agencies where enrolled therapists are seeing eligible clients. When study team members learn of a consent to contact from the therapist, they obtain verbal or written consent and assent from the guardian and client to record the encounter. If the therapist and client both request that a research team member sit with the recorders during the session, then a research team member will sit in the room and hold the recorder. Youth will be paid \$10 for allowing their therapy session to be audio-taped. Study participation for youth only entails recording their one session.

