Due to COVID-19, we have also decided to implement remote recruitment of therapists and clients. Research staff will recruit therapists by emailing them directly and introducing the study. If therapists are interested in participating in the study, research staff will consent therapists over the phone. Once consented, research staff will work with therapists to identify eligible clients using sequential sampling, which will ensure that we enroll clients receiving services across the treatment span. Therapists will introduce the study to eligible clients (and if necessary, guardians) via a virtual platform to obtain verbal consent (and if necessary, assent). If the client (and if necessary, guardian) are interested, research staff will enroll and consent clients through a virtual platform. Research staff will place the audio recorder next to the computer in a private room, press “record” on the audio recorder, close the door and leave the room. Therapists will notify the research staff through text message once the session is over. Youth will be paid with an electronic \$10 Amazon gift card for allowing their therapy session to be audio-taped.

All three conditions (described below) will be compared with direct observation (i.e., audio-recordings of each session). Therapists will be randomized to one of the three experimental measurement conditions. Therapists in the self-report condition will be asked to complete the self-report measure within 48 hours of the encounter, to ensure appropriate recall and also because that is typically when therapists are expected to complete their notes (personal communication, [name], Community Behavioral Health). Therapists in the other two conditions will

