complete chart-stimulated recall or behavioral rehearsal within one week of the encounter. We selected one week because therapists report receiving one hour of weekly supervision, suggesting that this time period is best in planning for future potential trials integrating these methods into community supervision. Therapists will be paid upon completion of their fidelity method (i.e., self-report, chart stimulated recall, behavioral rehearsal). Once a therapist enrolls three separate clients who each had a CBT session and has completed the fidelity measurement for each client, they have completed participation in this aim of the study (we estimate it will take a month to enroll three clients who each had a CBT session and complete fidelity measurements). More than three clients may be enrolled if a session was recorded and we find out that CBT was not used (e.g., the therapist thought CBT would be used in the session but it ended up being a crisis management session).

If assigned to the self-report condition, therapists will be asked to complete a brief self-report measure on their own time within 48 hours after each recorded session (once for each client; three times total; anticipated time = 30-60 minutes). Therapists can complete this measure via REDCap, a HIPAA compliant platform, or using paper-and-pencil, whichever is their preference. Therapists will be compensated \$50 for the completion of the self-report measure for their three clients. Additionally, to learn how to use this self-report measure, the research staff will ask therapists to engage in up to 30 minutes of training, for which they will be compensated an additional \$25.

If assigned to the chart-stimulated recall condition, therapists will be asked to meet with research staff for one hour. During that hour, therapists will bring the chart of each client that was recorded for a brief interview (approximately 20 minutes per client session). In this interview, therapists will be asked questions about different techniques they may have used in session with their client. Therapists will be allowed to use the chart for the client to spur their memory of the session but the research staff will not be allowed to view the chart. The research staff will ask to complete this interview with therapists within one week after the session was recorded with the client. Therapists will be compensated \$50 for the completion of chart-stimulated recall for three clients.

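### Does letting the randomised therapist call a taped session a crisis, and so have it left out, bias the comparison of the three fidelity methods?

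*Combined protocol and SAP*

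**What the plan says.** Under PROCEDURES, Aim 1, therapists consent at an agency meeting where the study team "will randomize therapists into one of the three measurement arms". Days and time blocks are then chosen at random and clients are enrolled until three count. The same section says of the three: "we will not include if the therapist identifies the session as a crisis of the week session".

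STUDY SAMPLE AND DATA SOURCE (repeated in section 5, Numbers of participants) says "we will ask therapists immediately following the session if this was a" crisis session or ordinary therapy, and that further clients may be enrolled to replace sessions that do not qualify. It adds a second criterion: "Sessions need to include at least ten minutes where the client is in the room". Aim 1 also has a replacement rule that names no judge: "More than three clients may be enrolled if a session was recorded and we find out that CBT was not used".

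The ANALYSIS PLAN states intent-to-treat and models the difference between direct observation and the assigned method, with a random effect for therapist. It does not list which taped sessions enter the model.

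For the remote route added because of COVID-19, the protocol says "research staff will consent therapists over the phone" but not when randomisation takes place. The point about timing is therefore firm only for the in-person route, although the crisis question itself is not confined to it.

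**The concern.** The therapist is the unit randomised, cannot be masked to the method, and is the person whose fidelity is being measured. That person's word, given after randomisation, can remove a taped session. The protocol gives no formal definition of a crisis, does not have the label confirmed from the tape, and plans no tally of dropped sessions by arm.

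The outcome is defined on sessions, so the sessions kept define what is compared. If therapists facing a role-play called more awkward sessions crises than therapists facing a questionnaire, and awkward sessions have larger or smaller discrepancies, the pairwise contrasts would compare differently selected sessions. The ranking of the three methods could then partly reflect selection.

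**Working it through.** **1. What decides whether a session counts.** Read together, the protocol's criteria are:

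- a separate client with a CBT session (Aim 1);
- not called a crisis by the therapist (Aim 1);
- at least ten minutes with the client present (STUDY SAMPLE AND DATA SOURCE);
- the assigned fidelity measure completed (Aim 1).

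A crisis is described informally, by contrast with ordinary therapy and by the example of a planned CBT session that turned into crisis management. The criteria are scattered, but an analyst can assemble the session set from them. Intent-to-treat then applies naturally to the randomised unit, the therapist.

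**2. Order of events and incentive.** The label is asked for immediately after the session. The self-report is due within 48 hours and the other two methods within one week. Coding typically comes one month later (SUBJECT RISKS). The label is therefore normally given before either score in the difference exists. On payment, "Therapists will be paid upon completion of their fidelity method", and participation in this aim ends only after three CBT sessions with completed measures. Calling a crisis means more recruitment, not less.

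**3. Condition for bias.** Let q be the share of an arm's sessions dropped, and d the mean discrepancy of dropped minus kept sessions, in SD. The kept mean is the overall mean minus q × d. With the same d in both arms, the bias has size |qA − qB| × d. If the same kind of session is dropped in each arm, the contrast is valid for non-crisis CBT sessions, which is the stated target.

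**4. Size.** The documents give no crisis rate, ICC or SD, so every input here is assumed. Therapists per arm: 45 (405/3 = 135; 135/3 = 45) or about 56 (the protocol's figure). With three sessions each and ICC 0.3:

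- SE of a contrast = √[2(1 + 2 × 0.3)/(3n)] = √(3.2/135) = 0.154 for n = 45, and √(3.2/168) = 0.138 for n = 56.
- Difference detectable with 80% power = 2.80 × SE = 0.43 and 0.39 SD.

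Formula in step 3: 10% v 10% gives 0; 10% v 5% with d = 0.25 gives 0.0125 SD; 20% v 5% with d = 0.5 gives 0.075 SD (nominal 5% test rejects 7.8% to 8.4% of the time).

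Simulation (8,000 runs per case), treating a crisis as low perceived session quality, with replacement to three sessions and quality–discrepancy correlation 0.3 to 0.5:

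| Dropped | Perceived v true quality | Bias (SD) | False positives |
|---|---|---|---|
| 15% v 15% | all cases | −0.002 to 0.004 | 4.7–5.6% |
| 10% v 15% | 0.5 to 0.7 | 0.005–0.023 | 4.5–5.3% |
| 10% v 15% | 1 | 0.019–0.036 | 5.1–5.6% |
| 5% v 20% | 0.5 | 0.026–0.046 | 5.4–6.1% |
| 5% v 20% | 0.7 | 0.036–0.064 | 5.8–7.6% |
| 5% v 20% | 1 | 0.060–0.101 | 6.8–12.0% |

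The worst case is 0.101/0.387 = 0.26, about a quarter of the detectable difference.

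**5. What a masked tape check would buy.** If 5% to 20% are dropped and 405 kept, 405 × 0.05/0.95 ≈ 21 to 405 × 0.20/0.80 ≈ 101 dropped tapes would need screening. In the extreme case (n = 56, 5% v 20%, perfect ranking, correlation 0.5; assumed coder cut 10%, coder–quality correlation 0.8), the bias is 0.102 SD with 12.1% false positives. Removing kept sessions that coders class as crises brings this to 0.077 SD and 8.8%. Adding back wrongly dropped sessions brings it to 0.016 SD and 5.3%, but that needs the assigned measure on those sessions. The plan provides for three measures per therapist, so dropped sessions would usually have none. The document is dated May 11, 2020 and enrolment is to "continue enrolling human subjects until mid-2020", so little could be collected prospectively.

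A tally by arm at 135 kept sessions would show 5% v 20% (7 of 142 v 34 of 169; power 0.98, or 0.87 with design effect 1.7). It would usually miss 10% v 15% (15 of 150 v 24 of 159; power 0.26, or 0.17).

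**The case for a change.** The strongest case for a change runs as follows. The arms ask different things of the therapist: a questionnaire with up to 30 minutes of training, a chart interview, or a role-play. Training could shift what one arm counts as CBT, and a role-play could make untidy sessions less attractive. The BACKGROUND reports poor agreement between therapist self-report and observers (a kappa of .22 in one study), so an unchecked therapist label sits oddly in this trial. Tapes are to be kept for three years after the study, so a check is feasible. Harsher inputs also give larger figures: with d = 1 SD, 20% v 5% gives 0.15 SD (rejection 16.4% to 19.2%) and 30% v 10% gives 0.20 SD (25.5% to 30.5%), both at ICC 0.3.

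Part of this stands. Differential labelling is possible, the text does not exclude it, and the wording on sessions found not to be CBT leaves open who else may judge.

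The rest does not carry the point. The kappa concerns fidelity ratings, not whether a session was a crisis. The harsher figures need a gap of 15 to 20 percentage points between arms and dropped sessions a full SD apart from kept ones, neither of which has any basis in the documents. Section 5 describes crises as often unforeseeable, which argues against strategic labelling. Feasibility of a check is not a reason for it when its main correction is mostly out of reach.

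**Conclusion.** No change is needed. Restricting the trial to non-crisis CBT sessions is a legitimate target, and the therapist is the only person placed to say at once that a replacement is required. Waiting for coding a month later would delay replacement and risk leaving therapists short of three sessions.

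Any bias is probably none to small: zero if labelling is alike across arms, at most about 0.04 SD for 10% v 15%, and about 0.10 SD in a deliberately extreme case. These figures rest on assumed drop rates, ICC 0.3, correlations of 0.3 to 0.5, and the assumption that a crisis behaves like a low-quality session. The documents supply none of these.

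What is unwritten is mainly detail. An analyst would collect the existing session criteria into one statement of the sessions analysed and report the number left out by arm and reason, as a matter of ordinary reporting. Masked re-screening and a sensitivity analysis would add coding work and, with no measure on most dropped sessions, correct only part of a bias that nothing in the documents suggests is present.

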If assigned to the behavioral rehearsal condition, therapists will be asked to meet with the research staff for one hour. During that hour, they will participate in a role-play demonstrating the strategies they used in session with the three clients that were recorded. Research staff will ask to complete this meeting within one week after the session was recorded with the client. Therapists will be compensated \$50 for the completion of behavioral rehearsal for three clients. If behavioral rehearsal takes longer than one hour, then the therapist will be compensated \$25 for each additional half hour it takes to complete the condition.

Aim 2: The research team will work closely with clinic leadership to collect cost data. The process begins by presenting the brief Drug Abuse Treatment Cost Analysis Program (DATCAP) materials to clinic leadership most familiar with the operations and financing of the program. After these personnel have reviewed the materials, conference calls are conducted between them and the researchers to formulate strategies for preliminary data collection and to answer questions. The researchers will provide clinic leadership with guidance regarding the type and source of resource use and cost information to gather. The researchers then conduct a site visit at each agency, which includes face-to-face meetings with clinic leadership and instrument completion. Cost analysis items include information about how much time is spent on each fidelity measurement method, the time it takes to develop the materials for the method, and the resources that are used for each condition (e.g., office room, computers). Please note, we have not included a consent form for Aim 2 of the study (i.e., assessing the cost-effectiveness of each fidelity measurement method) as this will be

accomplished by using the DATCAP to collect administrative level data on each organization; absolutely no individual level or identifying information will be collected as part of this economic evaluation.

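### Does one hour of recall or rehearsal for three clients conflict with the one-week limit on measurement?

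*Combined protocol and SAP*

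**What the plan says.** PROCEDURES, Aim 1, sets the timing for both staff-led methods: therapists "complete chart-stimulated recall or behavioral rehearsal within one week of the encounter". DURATION OF STUDY repeats the rule.

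The arm descriptions in the same section give each method one hour with research staff.

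- **Recall:** "therapists will bring the chart of each client that was recorded for a brief interview (approximately 20 minutes per client session").
- **Rehearsal:** "they will participate in a role-play demonstrating the strategies they used in session with the three clients that were recorded", followed by "Research staff will ask to complete this meeting within one week after the session was recorded with the client". Overrun is paid "for each additional half hour it takes to complete the condition".
- **Self-report:** completed within 48 hours of each recorded session, explicitly on three occasions.

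A therapist finishes Aim 1 after enrolling three clients and once he or she "has completed the fidelity measurement for each client". On duration, "we estimate it will take a month to enroll three clients who each had a CBT session and complete fidelity measurements".

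The ANALYSIS PLAN fits a first model with method, site and a random therapist effect. The second model adds time and time by method, to look for practice effects. Neither has a term for days from session to measurement, and time is not defined.

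**The concern.** The rehearsal paragraph speaks of a single hour, three clients and a single meeting. Read that way, the meeting cannot take place until the third session has been recorded, yet it must fall within a week of the first. Sessions spread over more than seven days would then break the limit for at least the first session, and the protocol does not say what happens in that case. By contrast, self-report is plainly tied to each session.

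The accuracy comparison would be at stake. The protocol justifies the 48-hour limit partly by recall, so it treats delay as relevant to accuracy. Extra delay would arise in two arms only and enter every contrast with self-report. It could also affect those two arms unequally, because only in the recall arm is there a memory aid: "Therapists will be allowed to use the chart for the client to spur their memory of the session". Finally, delay would be longest for the first session. If time in the second model means session order, the time-by-method term could not be read as practice alone.

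**Working it through.** **1. The plan's own figures.** Recall takes about 20 minutes per client session, and 3 x 20 = 60 minutes, the stated hour. The hour is therefore equally consistent with one sitting and with three short ones. DURATION OF STUDY gives 45 months at three therapists a month: 45 x 3 = 135 therapists, and 135 x 3 = 405 clients, the stated number.

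**2. What a single sitting would require.** The meeting is on or after the day of the last session and within 7 days of the first. So last session minus first session must be at most 7 days. This is arithmetic and holds if the hour is one meeting.

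**3. How often that would fail.** The documents give no session spacing, so two assumptions are shown. Both place one meeting on the day of the last session.

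(A) Three independent session dates, uniform over S days. With r = min(1, 7/S), P(all three in window) = 3r² − 2r³. For S = 14, r = 0.5, and 0.75 − 0.25 = 0.50.

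(B) Independent exponential gaps of mean g = S/4, which match the mean first-to-last interval of S/2 under (A). With x = 7/g, P = 1 − exp(−x)(1 + x). For S = 14, x = 2, and P = 0.594.

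| S (days) | (A) all in window | (B) all in window |
|---|---|---|
| 7 | 100% | 91% |
| 14 | 50% | 59% |
| 21 | 26% | 38% |
| 30 | 14% | 24% |

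The last row is extreme. The month includes measurement, so a 30-day spread of sessions leaves no time for it. Taking 7 days off gives S = 23, and (A) gives 22%.

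**4. Delay and session order under (A).** In units of S, the mean delays for sessions 1, 2 and 3 are 1/2, 1/4 and 0, and the mean squares are 0.3, 0.1 and 0. So Var(delay) = 0.4/3 − 0.0625 = 0.0708, Var(order) = 2/3 and Cov = −1/6. The correlation is −0.1667/√(0.6667 x 0.0708) = −0.77. This follows from the single-meeting premise alone. With one contact per session and delay uniform on 0 to 7 days, the correlation is 0.

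**5. The two readings side by side.**

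- *One sitting:* the rehearsal paragraph places all three clients within the hour and refers to one meeting. Self-report is said to be done three times, and no such words appear for the other arms.
- *Total of per-client contacts:* the one-week rule is written for one encounter, and both arm-level deadlines refer to one session with one client. Recall time is per client session. Completion is defined client by client. Rehearsal overrun is paid by the time needed to complete the condition. The self-report payment is a total for three clients, although that measure is done on three occasions. A model for practice effects fits repeated occasions more naturally than one sitting.

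Under the second reading each delay can be at most 7 days for any spacing, and total time is still 60 minutes.

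**6. Can sessions cluster?** Yes. Therapists report about 30 encounters a week, and eligible clients are approached within randomly selected time blocks until three are enrolled. Three sessions in a week are feasible, though the sampling scheme does not require it.

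**7. Reach of a wording change.** The document is dated 11 May 2020, and enrolment runs to mid-2020. Taking that as 15 June to 15 July gives 1.15 to 2.14 months. At three therapists a month, 3.5 to 6.4 therapists remain. Two thirds of these, 2.3 to 4.3, would be in the recall or rehearsal arms.

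**The case for a change.** The strongest case for a change is that a measurement procedure should not admit two readings when the study outcome is the accuracy of that measurement. The rehearsal paragraph, taken alone, does read as one sitting. If agencies worked that way, the first session could be rehearsed well after a week, in two arms only, and nothing in the models would reveal it. Stating one contact per session would leave the total hour and payment unchanged, and describing delay by arm would be informative for everyone already enrolled.

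The ambiguity stands, and so does the seven-day arithmetic under one sitting. The rest carries less weight. The one-week limit is explicit and applies to each encounter, so single meetings that breach it would be departures from the protocol rather than a consequence of it. The month does not show that sessions are widely spaced. The percentages depend entirely on assumed spacing and run from no misses to most. No effect of delay on the difference score has been shown: forgetting could shift its mean or only widen its variance.

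Nor do the planned models need a delay term. Delay up to a week is part of the method as intended for use, since the interval was chosen to mirror weekly supervision. Delay is also largely set by arm, so adjusting for it across arms would remove part of what is being compared. A descriptive summary of delay would be harmless, but it would leave the primary analysis as it is, and the documents do not say that session and measurement dates were both kept.

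**Conclusion.** No change is needed. This is loose wording that staff can resolve by applying the one-week rule as written, encounter by encounter. The passages conflict only if the hour must be a single meeting and the three sessions span more than seven days; the documents establish neither.

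On the assumption of single meetings, compliance for all three sessions would run from 100% to 14% of therapists for uniform session dates over 7 to 30 days, and from 91% to 24% with exponential gaps. These figures show sensitivity to spacing and are not estimates for this trial. With per-client contacts the conflict disappears, as does the tie between delay and session order.

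The size and direction of any bias are unknown, the intent-to-treat contrasts would stay primary in any case, and clearer wording would affect roughly 2 to 4 remaining therapists at the planned pace. The judgement rests on the stated limit being followed. Records of single meetings held routinely more than a week after the first session would matter when the results are interpreted.
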